## II.GLOSSARY OF ABBREVIATIONS

5-ALA	5-Aminolevulinic acid
5-FU	5-Fluorouracil
ACCP	American College of Chest Physicians
ADCC	Antibody Dependent Cellular Cytotoxicity
AE	Adverse Event
AJCC	American Joint Committee on Cancer
ALT (SGPT)	Alanine aminotransferase
ANC	Absolute neutrophil count
aPTT	Activated Partial Thromboplastin Time
AST (SGOT)	Aspartate aminotransferase
AUC	Area under the plasma concentration-time curve
β-HCG	Beta-Human Chorionic Gonadotropin
BOR	Best Overall Response
BP	Blood pressure
BUN	Blood Urea Nitrogen
CALGB	Cancer and Leukemia Group B
CCL2	Chemokine ligand 2
CI	Confidence interval
CR	Complete Response
CRF	Case Report Form(s)
CSR	Clinical Study Report
CT	Computed Tomography
CTLA-4	cytotoxic T-lymphocyte antigen-4
CTV	Clinical Tumor Volume
CNS	Central Nervous System
CVAD	Central Venous Access Device
DDI	Drug-Drug Interaction
DNA	Deoxyribonucleic Acid
DSMB	Data and Safety Monitoring Board
DVH	Dose-Volume Histograms
DVT	Deep Vein Thrombosis
ECG	Electrocardiogram
ECOG	Eastern Cooperative Oncology Group
EEA	European Economic Area
EEG	Electroencephalogram
EGFR	Epidermal Growth Factor Receptor
EIAEDs	Enzyme-inducing Antiepileptic Drugs
EORTC	European Organization for Research and Treatment of Cancer
ePD	Early Progressive Disease
ESMO	European Society for Medical Oncology
ESF	Eligibility Screening Form
EU	European Union
FASL	FAS ligand
GBM	Glioblastoma
GCP	Good Clinical Practice

G-CSF	Granulocyte colony-stimulating factor
GM-CSF	Granulocyte-macrophage colony-stimulating factor
GI	Gastrointestinal
GTV	Gross Tumor Volume
Gy	Gray
H0	Null hypothesis
H1	Alternative hypothesis
IC	Informed Consent
ICH	International Conference on Harmonization
ICRU	International Commission on Radiation Units and Measurements
IDH	isocitrate dehydrogenase gene
IHC	Immunohistochemistry
II-2	Interleukin-2
IL-6	Interleukin-6
II-10	Interleukin-10
INR	International Normalized Ratio
IMP	Investigational Medicinal Product
IMRT	Intensity-Modulated Radiation Therapy
irAEs	Immune –Related Adverse Events
irRC	Immune-related Response Criteria
iRANO	Immunotherapy Response Assessment in Neuro-Oncology
IRB/IEC	Institutional Review Board/Independent Ethics Committee
IRF	Independent Review Facilities
ISH	In situ hybridization
ITT	Intent To Treat
IV	Intravenous
IVRS	Interactive Voice Response System
KPS	Karnofsky performance Status
LDH	Lactate Dehydrogenase
LMWH	Low Molecular Weight Heparin
MGMT	O6-methylguanine-DNA methyltransferase
MMSE©	Mini Mental State Examination
MoAb	Monoclonal Antibody
MRI	Magnetic Resonance Image
mRNA	Messenger RNA
MTD	Maximum Tolerated Dose
muMAb	Murine Monoclonal Antibody
NCCN	National Comprehensive Cancer Network
NCDB	National Cancer Data Base
NCF	Neurocognitive Function
NCI	National Cancer Institute (USA)
NCIC	National Cancer Institute of Canada
NCI-CTC	National Cancer Institute-Common Toxicity Criteria
NCI-CTCAE	National Cancer Institute-Common Toxicity Criteria for Adverse Events
NCIC-CTG	National Cancer Institute of Canada Clinical Trials Group
NSAID	Non-steroidal Anti-Inflammatory Drug
NSCLC	Non-small Cell Lung Cancer
NYHA	New York Heart Association

OR	Overall Response
ORR	Objective response rate
OS	Overall survival
PBMC	Peripheral Blood Mononuclear Cell
PD	Progressive disease or Pharmacodynamics
PD-1	programmed death 1 (receptor)
PD-L1	programmed death ligand 1
PE	Pharmacoeconomic
PFS	Progression free survival
PICC	Peripherally Inserted Central Catheter
PK	Pharmacokinetic
PIGF	Placental Growth Factor
p.o.	Oral administration
PR	Partial Response
PS	Performance Status
psPD	Pseudo progression
PT	Prothrombin Time
PTV	Planning Tumor Volume
q.d.	Once daily administration
q.w.	Once a week
q2w	Once every 2 weeks
q3w	Once every 3 weeks
RCR	Roche Clinical Repository
RBC	Red Blood Cell
RNA	Ribonucleic Acid
RPA	Recursive Partitioning Analysis
RPLS	Reversible Posterior Leukoencephalopathy Syndrome
RT	Radiotherapy
RTOG	Radiation Therapy Oncology Group
RT-PCR	Reverse transcription-polymerase chain reaction
SAE	Serious Adverse Event
SD	Stable Disease
SNP	Single Nucleotide Polymorphism
SPD	Sum of the Product of biperpendicular Diameters of the measurable enhancing lesions
SRS	Stereotactic Radiosurgery
SWFI	Sterile Water for Injection
T1/2	Half-life
t.b.d.	To be determined
TE	Tracheoesophageal
TEAE's	Treatment Emergent Adverse Events
TGF-B	Transforming Growth Factor
TMA	Tissue Microarray
TMZ	Temozolomide
TO	target occupancy
Treg	regulatory T cell
TTP	Time to Tumor Progression
ULN	Upper Limit of Normal

UPC	Urine Protein/Creatinine Ratio
USP	United States Pharmacopeia
Vc	Volume of the Central Compartment
VEGF	Vascular Endothelial Growth Factor
WBC	White Blood Cell
WHO	World Health Organization

### III. SYNOPSIS OF PROTOCOL

**Version Number:** 5

**Protocol Title:** Avelumab in patients with newly diagnosed Glioblastoma Multiforme

**Sponsor:** Clinique Neuro-Outaouais

**Indication:** Patients with newly diagnosed Glioblastoma Multiforme

**Study Type:** Single center, phase 2, open-ended, open label, addition of avelumab to standard therapy

#### Objectives

##### **Primary Objectives:**

To determine the safety and tolerability of avelumab administered as 10mg/kg IV q2weeks in patients receiving standard therapy for newly diagnosed GBM.

##### **Secondary objectives:**

To determine the impact of the addition of avelumab at a dose of 10mg/kg IV Q2weeks in patients receiving standard therapy for newly diagnosed GBM on overall survival (OS), progression free survival (PFS) and other antitumor activity parameters according to the immunotherapy Response Assessment for Neuro-Oncology (iRANO) (1) at 52 weeks and every 52 weeks thereafter.

##### **Exploratory objectives:**

To explore biomarkers that could predict treatment response to avelumab such as: the tumor immunoscore, presence and extent of PD-L1 expression on tumor cells and microglia/macrophages within the tumor

To correlate the OS and PFS in relation to the baseline value and the change from baseline to week 52 visit and every 52 weeks /or end of study visit (depending on whether the latter occurs before or after week 260) neurocognitive function as measured by the evoked potential P300 (normal), the baseline corticosteroid dose, the total cumulative corticosteroid dose over the whole study duration, the total cumulative temozolomide dose per BSA since diagnosis and the presence and severity of immune related adverse events (irAE's).

To assess and compare above mentioned biomarkers in tissue samples from patients with second surgical resection ie treatment failures.

To assess in this GBM population the duration of pseudoprogression and the lagtime needed for immunotherapy to become effective.

**Study Design:** This is a single center, phase 2, open-ended, open label, add-on, single dose study in patients receiving standard therapy for newly diagnosed GBM with

a projected duration of 5 years (260 weeks). In total 30 patients who meet the entry criteria will be entered into the study within 3 weeks of finishing their last day of combined radiotherapy/temozolamide. Avelumab will be initiated concurrently with the initiation of the first 5 days, monthly cycle of temozolamide and continued until the occurrence of a termination event defined as one of the following: 1) clinical evidence of neurological deterioration resulting in an ECOG score of at least 3 or more, unexplained by other comorbidities, unchanged by an increase in corticosteroid dose and sustained for at least two weeks or 2) treatment emergent adverse event (TEAE) of grade 3 or more or 3) withdrawal of patient consent.

A local pathology report will constitute adequate documentation of histology for study inclusion.

The tumor block used for diagnosis of GBM must be collected for each patient and sent for MGMT assessment (if not already done), biomarker and immunoscore analysis. The availability of these samples is mandatory for the baseline visit.

Paraffin embedded blocks containing formalin-fixed tumor tissue representative of the glioblastoma diagnosis is the preferred sample (if available, and of sufficient quality), otherwise, a partial tumor block, or pathology material should be sent. If surgery was not performed but biopsy was performed (or if it is not possible to send FFPE tumor tissue blocks) at least 10 unstained, uncovered slides must be sent.

The study will consist of 3 different phases: a Combination Phase, a Monotherapy Phase and an Extended Safety Follow-up Phase

**Combination Phase:** Upon completion of the standard combination therapy of radiotherapy (total dose 60 Gy, administered as daily 2Gy fractions, 5 days/week or as per local protocol) and temozolamide (75 mg/m^2/day p.o. qd) and a treatment break of no more than 21 days, the combination phase will start. Patients will receive temozolamide and avelumab for 6 cycles of 28 days each. During the 1st cycle Temozolamide will be given the first 5 days at a dose of 150mg/m^2/day p.o. In the next cycle, the temozolamide dose should be escalated to 200/mg/m^2 if permitted by the patient's hematological and non-hematological toxicity profile (as per NCI-CTC AE version 5). The temozolamide dose will be adjusted according to hematological and non-hematological toxicity as per temozolamide's product monograph (appendix 4). Avelumab will be administered on day 1 and day 15 of each cycle at a dose of 10mg/kg IV. Avelumab therapy will be withheld according to the occurrence and severity of avelumab emergent adverse events as per table 3. Patients will continue the combination of temozolamide (150-200mg/m^2 per day PO X5 days Q28days) and avelumab (at 10mg/kg dose, IV on days 1 and 15 per cycle) until 6 cycles are completed or until the occurrence of a termination event.

**Monotherapy Phase:** Upon completion of the Combination Phase or upon stopping temozolamide because of temozolamide related toxicity/tolerability issues or patient choice, the patient will continue into the avelumab Monotherapy Phase. Avelumab 10mg/kg IV Q2weeks will be continued as monotherapy until the occurrence of a termination event.

Patients who experience irAE's may according to table 3 directives have their avelumab therapy suspended.

The use of Bevacizumab or re-irradiation will not be allowed in the study and will be considered as evidence of disease progression.

Patients will be promptly informed upon confirmation of disease progression as per the new iRANO criteria. They will be offered to pursue with the avelumab therapy as monotherapy or in combination with other therapies or to withdraw from therapy and enter the extended safety follow up phase. They will need to be reconsented before allowed to continue with the avelumab therapy.

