#### **Prognostic Factors**

Mutations of the isocitrate dehydrogenase gene (IDH) 1 or 2 are hallmarks of low- grade glioma. When found in GBM (5 to 10% incidence) they suggest a secondary transformation i.e. secondary GBM and portend a better prognosis independent of MGMT methylation (4).

Methyl-guanine methyl transferase (MGMT) is involved in DNA repair. Its epigenetic silencing by gene promoter methylation leads to a greater vulnerability of the GBM to alkylating chemotherapy induced DNA damage (5). The improved outcome in GBM patients with methylated MGMT has been demonstrated repeatedly (6). MGMT methylation in patients with GBM (35% incidence) undergoing standard therapy conferred a definite survival advantage with 62% 18-month survival compared to 8% (7). Other prognostic factors include radical resection, younger age (<50years), good performance status and an intact neurological function.

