## **2.2. Immunoscore**

It has become accepted that the host immune contexture has significant value in tumor prognostication and grade. The Immunoscore quantifies two lymphocytes population: CD3/CD45RO and CD3/CD8 within the tumor core and the invasive margin and assigns a score of 0 to 4 with the latter indicative of high density of immune infiltration. This score has been shown in two cohorts of colorectal cancer patients (n=602) to be highly predictive of tumor recurrence and survival at 5 years (38).

In this study using an anti-PD-L1 in patients with GBM the predictive power of the Immunoscore and thus its potential future use as a biomarker in this cancer population will be explored.

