### **7.1. Inclusion criteria**

1. Signed informed consent
2. Age  $\geq$  18 years
3. Present with newly diagnosed supratentorial Glioblastoma (GBM) with a tissue diagnosis that has been established following either a surgical resection or biopsy. This includes treatment-naïve - (chemotherapy and radiotherapy)- patients with prior diagnosis of a lower grade astrocytoma that has been upgraded to a histologically verified GBM
4. Karnofsky performance score of 70 or higher
5. Patients entering the study must be on a stable dose of no more than 12 mg (maximum) of Dexamethasone (or equivalent) daily for symptoms related to cerebral edema
6. Will be or is undergoing or has received the standard therapy of chemo radiation therapy (60Gy in 30 fractions of 2Gy/day or as per local protocol with concurrent temozolomide of 75mg/m^2 per day PO or as per local practise) no more than 21 days ago
7. Has not yet begun but will begin standard monthly temozolomide therapy
8. Patient must have at least 1 formalin fixed paraffin embedded tumor tissue block representative of glioblastoma available for biomarker analysis and determination of MGMT status (if not already done). If tumor block is not available or not of adequate quality, sufficient pathology material, representative of glioblastoma, must be available
9. Adequate hematological function defined by absolute neutrophil count (ANC)  $\geq$  1.5  $\times$  10^9/L, platelet count  $\geq$  100  $\times$  10^9/L, and hemoglobin  $\geq$  9 g/dL (may have been transfused)
10. Adequate hepatic function defined by a total bilirubin level  $\leq$  1.5  $\times$  the upper limit of normal (ULN) range and AST and ALT levels  $\leq$  2.5  $\times$  ULN for all subjects

11. Adequate renal function defined by an estimated creatinine clearance  $\geq$  30 mL/min according to the Cockcroft-Gault formula (or local institutional standard method)
12. Negative serum pregnancy test at screening for women of childbearing potential

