1.3.3. Exploratory

The incidence of PD-L1 expression on tumor cells and microglia/macrophages within the tumor will be determined and correlated to OS and PFS and other iRANO endpoints

The histological immunoscore will be determined and tested for association with OS, PFS, and other iRANO endpoints using logistic regression.

The association between 12 months OS and PFS with baseline neurocognitive function as measured by the evoked potential P300 (normal), the baseline corticosteroid dose, the average daily corticosteroid dose over the whole study duration, the extent to which patients complete the full 6 cycles of temozolomide based on temozolomide toxicity and the incidence and severity of treatment related irAE's will be tested using logistic regression.

The change if any in histological markers on tissue obtained from repeat resection

The estimation of the time period in which radiological progression was seen in clinically stable patients whose imaging was subsequently followed by radiological stabilization or regression

The estimation of the time period in clinically stable patients before radiological evidence of tumor regression occurred

The change in P300 will be determined and correlated with clinical outcomes as per iRAN

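### The immunoscore needs tumour core and invasive margin, but nothing secures a margin in biopsy tissue, and the immunoscore regression has no surgery-type term

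*Protocol*

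**What the plan says.** - **Score.** Protocol 2.2 builds the immunoscore from two lymphocyte populations "within the tumor core and the invasive margin and assigns a score of 0 to 4". The supporting evidence is from colorectal cancer (n=602). No adaptation to glioblastoma or to biopsy tissue is described.
- **Patients.** Protocol 7.1 admits a "tissue diagnosis that has been established following either a surgical resection or biopsy".
- **Tissue.** The Synopsis (Study Design) and Protocol 9.3.8 require tissue from each patient. "Paraffin embedded blocks containing formalin-fixed tumor tissue representative of the glioblastoma diagnosis is the preferred sample"; otherwise part of a block or other pathology material may be sent. The clause beginning "If surgery was not performed but biopsy was performed" asks for a minimum of ten unstained slides, and it also covers patients for whom no block can be sent. A margin is not required for any of these sample types.
- **Prognosis.** Protocol 1.1.1: "Other prognostic factors include radical resection". No effect size is given.
- **Analysis.** SAP 1.3.3 (and Protocol 12.3.3): "The histological immunoscore will be determined and tested for association with OS, PFS, and other iRANO endpoints using logistic regression". No covariate, significance level or missing-margin rule is stated.
- **Stratification.** Radical resection versus biopsy is a stratification factor in the Synopsis (secondary endpoints), Protocol 5.2 and 12.3.2, and SAP 1.3.2. It is not repeated in the exploratory section.
- **Second surgery.** An exploratory objective reads "To assess and compare above mentioned biomarkers in tissue samples from patients with second surgical resection ie treatment failures".

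**The concern.** A score that counts two regions cannot be compared across patients unless both regions were looked at, or there is a rule for when one is absent. A biopsy may hold no identifiable margin. With no rule in the plan, whoever scores the slides has to choose one, in an open-label single-centre study where outcomes may already be known. Counting an absent margin as zero limits that patient to 2 of 4 points. Leaving the score missing removes such patients.

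Under the first choice, surgery type lowers the score and, by the protocol's own account, also predicts survival. An association between immunoscore and survival could then reflect the extent of surgery alone. Protocol 2.2 wants to judge the score as a possible future biomarker, and a positive result could not be told apart from resected patients living longer. The re-resection comparison has a related weakness: a biopsy followed by a resection could show a rise that comes only from the type of specimen.

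**Working it through.** **Plan's own figures.** None exists for the immunoscore analysis. The general precision statement for n=30 does reproduce: 1.96 × √(0.25/30) = 0.179 (below 18%) and 1.96/√30 = 0.358 (0.36 SD).

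**Inputs from the documents.** n = 30; one-year OS 60% (SAP 1.3.2); four region-by-population cells (Protocol 2.2).

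**Assumptions, because the documents give no values.** Biopsy share f = 20, 30 or 40%. Biopsy one-year OS = 50, 40 or 30%. Each cell is high with probability 0.5, unrelated to survival. Margin cells are set to 0 in every biopsy. The outcome is one-year OS, tested by a logistic likelihood-ratio test at a nominal two-sided 5%.

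**Step 1, score shift.** Mean score is 4 × 0.5 = 2 in resected patients and 2 × 0.5 = 1 in biopsied patients. The same arithmetic gives a one-point mean rise for a biopsy-then-resection pair with no biological change.

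**Step 2, survival gap.** Resected OS = (0.60 − f × biopsy OS)/(1 − f). For f = 0.30 and biopsy OS 0.40: (0.60 − 0.12)/0.70 = 0.686.

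**Step 3, rejection rate with no true effect, no surgery-type term (3,000 simulated trials per setting).**

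| Biopsy share | Biopsy OS 50% | 40% | 30% |
|---|---|---|---|
| 20% | 7.0% | 8.1% | 11.3% |
| 30% | 7.8% | 10.4% | 17.5% |
| 40% | 9.0% | 15.8% | 29.8% |

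At a 30% share the median odds ratio per point is 1.13, 1.28 and 1.48. A separate set of 4,000 trials per setting agrees within 2 percentage points.

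**Step 4, remedies in the same settings.** Adding a resection/biopsy term, restricting to resected patients, treating margin-less samples as not evaluable, or using a core-only score each gives about 5-8%. The small-sample baseline of this test is itself about 5-7%. If all biopsies are dropped, n falls to 30 × (1 − f) = 24, 21 or 18.

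**Step 5, milder assumptions.**
- Margin zeroed in only half of biopsies: 6-13%.
- 10% biopsies, all zeroed: 6-7%.
- Score uniform on 0-4, one point lost per biopsy, 20% biopsies, 20-point survival gap: odds ratio 1.06, rejection 6%.
- Score not shifted in biopsies, or no survival gap: odds ratio about 1.00.
- Extreme case of every biopsy scored 0, 40% biopsies, 40-point gap: odds ratio 1.50, rejection about 35%, falling to about 7% with a surgery-type term.

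**The case against.** The strongest reply is that the harm is hypothetical. No text says that a biopsy lacks a margin or that an absent margin counts as zero, and the biopsy share and survival gap are assumed. If margin-less samples are simply not evaluable, the result is missing data and no false association. All of that stands.

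Second, resection versus biopsy is already a planned stratification factor, and Protocol 9.3.1.1 collects surgical details at screening. Protocol 5.2 applies the factor to the iRANO endpoints, which the immunoscore is tested against. This is a fair point, but every statement of it falls under secondary endpoints and none extends it to the immunoscore regression. Stratifying would also not define the score when a region is absent.

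Third, the analysis is exploratory. The SAP says the focus is descriptive, no decision rule attaches to this test, and immunoscore is listed beside PD-L1 without ranking. That limits the weight of the point, and the 5% level is only a yardstick.

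A reader might also fault slides and partial blocks as such. The documents do not support that: slides can come from a resection specimen and may hold both regions, while a full block need not contain margin.

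**Conclusion.** The point holds as a gap in the plan. There is no rule for samples without an invasive margin, and nothing states that the immunoscore analysis accounts for surgery type, so the association may be confounded.

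A reader might infer that biopsied patients cannot be scored on the 0-4 scale, or that a false association is built in. Neither follows. Bias needs both a lower score in biopsies and a survival difference by surgery type. The documents call radical resection prognostic without giving a size, and they are silent on how biopsies would score.

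The 7-30% range rests on margins scored 0 in all biopsies, 20-40% biopsies and biopsy one-year OS of 30-50%. Under mild assumptions the rate is close to baseline. The re-resection concern is the same in kind but cannot be sized, because the number of biopsy-then-resection pairs is unknown. Given the exploratory status, this is a modest point that is worth correcting because the correction is nearly free.

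**What to change.** In SAP 1.3.3 and Protocol 12.3.3:

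1. Treat the full 0-4 score as evaluable only when both tumour core and invasive margin are identified. Never score an absent margin as 0. Report how many samples are not evaluable, by surgery type.
2. Extend the existing resection/biopsy factor to the immunoscore analysis, as a model term or by showing the association within resected patients. The factor names only radical resection and biopsy, so state where partial resections belong.
3. Report a core-only score, computed the same way wherever core is identified, as a sensitivity analysis. It should not displace the score that Protocol 2.2 sets out to explore: it is coarser, and it assumes that core can be recognised in biopsy material.
4. At re-resection, compare only the regions present in both specimens.

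The cost is some SAP and protocol wording and one extra recorded field for the regions present. No new tissue, assay or patients are needed. The downside is fewer evaluable full scores: 18 to 24 of 30 if 20-40% are biopsies and none holds a margin.
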